#### 5.5.4.7 Diagnostic Confidence

Descriptive statistics for the *diagnosis of the MRI* and the *level of diagnostic confidence* will be presented by contrast agent group for each dose of P03277; off-site and on-site reader's outcomes will be separately analyzed.

The tables and listings that will be displayed are detailed in Sections 6.1.2, 2.7 and 6.2.6.2 respectively.

CONFIDENTIAL	FORM STATISTICAL ANALYSIS PLAN N° GDX-44-004 VERSION 1.0 DATED: 09JAN2018 
[REDACTED]
	

 Page 38 / 60
--------------	--	---

#### 5.5.4.8 Overall Diagnostic Preference

The *level of overall diagnostic preference of images* will be displayed as follows:

- P03277 is preferred to MultiHance®.
- No difference between the 2 contrast agents.
- MultiHance® is preferred to P03277.

For each off-site reader, the overall diagnostic preference will be tabulated for each dose of P03277. Each dose of P03277 will be compared to MultiHance® by a Wilcoxon signed-rank test.

SAS® procedure used for this analysis will be:

```
proc univariate data=XXX;
  class reader dose;
  var diff;
  output out=XXX probs=PROBS;
run;
```

The *reason of this preference* (at least one among a pre-specified list of 6) will be displayed according to the contrast agent preferred.

The tables and listings that will be displayed are detailed in Sections 6.1.2.2.8 and 6.2.6.2 respectively.

#### 5.5.4.9 Impact on Subject Treatment Plan

The impact on subject treatment plan will be assessed by on-site radiologists and will be summarized for each dose of P03277 by contrast agent group.

The table and the listing that will be displayed are detailed in Sections 6.1.2.2.9 and 6.2.6.2 respectively.

### 5.6. Safety Evaluation

All safety parameters will be analyzed using the Safety Set on the following contrast agent groups: “P03277 0.025 mmol/kg”, “P03277 0.05 mmol/kg”, “P03277 0.1 mmol/kg”, “P03277 0.2 mmol/kg”, “Total P03277” and “MultiHance®”. A subject will be included in a group as soon as he actually received the displayed contrast agent, either at the 1st or the 2nd period.

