
 
➤ The first subset will include the first subject of each study center. Subjects will be administered at 0.05 or 0.1 mmol/kg BW of P03277 and MultiHance®, 0.1 mmol/kg BW. Images from this subset of subjects will be used to provide training images for the independent blinded off-site readers, to ensure that the imaging protocol/acquisition sequences has been appropriately programmed, and that the MR images produced can be transferred to the core laboratory. Consequently, these subjects will not be included in the efficacy analysis but only for the safety assessment.
 
➤ The second subset will be composed of all subjects (except the first one of each site) selected by the sites. Subjects will be administered at 0.025, 0.05, 0.1, 0.2 mmol/kg BW of P03277 and
 
	

 CONFIDENTIAL	Protocol No. GDX-44-004 Version No. 2.0 (Protocol including amendment n°1) Date: 11 July , 2016	[REDACTED] Page 3 / 84
----------------------------------------------------------------------------------------------------------	----------------------------------------------------------------------------------------------------------	---------------------------

0.1 mmol/kg BW of MultiHance®.

The subjects will be randomly assigned to one of the doses of P03277 and to one series of 2 MRIs performed each at two study visits separated by a wash out period of 2 days minimum up to 14 days. The series are related to the use of contrast agent: one series will have P03277 at visit 2 and MultiHance® at visit 4 or vice versa for the other series.

The randomization scheme will allocate subjects to the two P03277 treatment arms in a 1:1 ratio for the first subset of subjects and to the four P03277 treatment arms in a 1:1:1:1 ratio for the second subset of subjects. The P03277 will be injected at a rate of 2 mL/second.

The same dose of MultiHance®, 0.1 mmol/kg BW by single IV injection at a rate of 2 mL/second, will be injected to all subjects.

The investigator and the subject will remain blinded to IMPs allocation (nature of the IMPs and order of the IMP injection) as well as the dose of P03277 used. A designated unblinded site staff member will be in charge of preparation and administration of the IMPs.

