### 3 STUDY DESIGN

#### 3.1 Protocol Description

The purpose of this phase IIb study is to determine an effective and safe clinical dose of P03277 injection for CNS lesion detection and visualization by conventional steady-state CNS imaging. Therefore, CNR, a well-known quantitative parameter directly related to contrast medium/GBCA efficacy, has been chosen as the primary endpoint in order to have a precise determination of P03277 clinical dose. Clinically meaningful parameter as lesion visualization which correlates with CNR will also be assessed, as a secondary primary endpoint.

This is a multi-center, international, prospective, double-blind, randomized, controlled, parallel dose groups, cross-over with comparator study in male and female subjects presenting with either known or highly suspected focal areas of disruption of the BBB (e.g. primary and secondary tumors, focal inflammatory disorders), who are scheduled to undergo a routine contrast-enhanced MRI of the CNS.

This study will be conducted in approximately 40 centers worldwide.

Two subsets of subjects (subset 1 and subset 2) will be included in the study. Subjects of the two subsets will be randomly assigned to one of the doses of P03277 and to one series of 2 MRIs performed each at two separate study visits (see [Figure 1](#)).

The first subset will consist of the first subject of each site. Indeed, in order to provide training images for the independent blinded off-site readers, to ensure that the imaging protocol/acquisition sequences has been appropriately programmed, and that the MR images produced can be transferred to the core laboratory, a dedicated subset of subjects (subset 1) will be enrolled for this purpose. Subjects of the subset 1 will be administered at 0.05 or 0.1 mmol/kg of P03277 with a 1:1: ratio and at 0.1 mmol/kg of MultiHance® and will perform all the study evaluations and safety assessments (see [Figure 1](#)). The two P03277 doses have been chosen as they are surrounding the potential targeted clinical dose. These subjects will not be considered for the efficacy analysis but only for the safety assessment. A maximum of forty (40) subjects (depending of the number of participating sites) will be included in the subset 1.

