### 5.3 Condition of Investigational Medicinal Product allocation

#### 5.3.1 *Investigational Product(s) Allocation / Randomization*

At visit 2, the subjects will be randomly assigned to one of the doses of P03277 and to one series of 2 MRIs performed each at two study visits separated by a wash out period of 2 days minimum up to 14 days. One series consists of the use of P03277 as contrast agent at visit 2 and MultiHance® at visit 4. The second series consists of the use of MultiHance® at visit 2 and P03277 at visit 4.

The P03277 dose to be injected to the subjects will be attributed by randomization (according to randomization list) at the time of visit 2 simultaneously with the MRIs order allocation.

The randomization scheme will allocate subjects to the two P03277 treatment arms (0.05 or 0.1 mmol/kg BW) in a 1:1 ratio for the first subset of subjects and to the four P03277 treatment arms (0.025, 0.05, 0.1 or 0.2 mmol/kg BW) in a 1:1:1:1 ratio for the second subset of subjects. The P03277 will be injected at a rate of 2 mL/second.

The same dose of MultiHance®, 0.1 mmol/kg BW by single IV injection at a rate of 2 mL/second, will be injected to all subjects.

The randomization will be done via IWRS with a stratification factor for the subset 2: presence of brain metastasis (yes/no) and performed in blocks to prevent unequal treatment allocation. For the subset 2, subjects with brain metastasis will be included at a minimum of 20% in each dose group of P03277.

The study design and the injection of the IMPs require identifying before the study start, two separate teams in each study site. One will manage the blinded data and another one will be unblinded and will be in charge of the IMPs preparation and administration. The unblinded staff will have to document in a separated subject's file all the unblinded information related to the IMPs and will have to complete a dedicated eCRF pages with restricted access.

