## 8 NUMBER OF SUBJECTS

Based on the hypothesis below, a total of 280 subjects will be enrolled in the study:

- First subset: maximum 40 subjects (depending of the number of participating sites) on the basis of 1 subject per site.
- Second subset: 240 subjects based on the following assumption: the study aims at detecting a minimum of 30% increase of CNR for at least one of the four tested dose of P03277 compared to control arm MultiHance® at dose of 0.1 mmol/kg BW. A sample size of 50 evaluable subjects per group is required to obtain a power of at least 90%, using a t-test of a normal mean difference with a 1-sided significance level of 0.025 (Holm's step-down method in a Multiple Comparisons Design) and a common standard deviation of 3.01. Therefore, a minimum of 50 evaluable subjects per dose group and a minimum of 200 evaluable subjects in total will have to be enrolled in this study.

An evaluable subject is defined as a randomized subject, 2 contrast agents administered, having undergone 2 complete, assessable and interpretable MRI examinations, presenting with at least one enhancing lesion of minimum 5 mm (long axis).

It is anticipated that some of the subjects will not complete both MRI evaluations. To offset this, an additional 10 subjects per group will be added to the 50 required leading to a total of 240 randomized subjects.

The number of non-evaluable subjects will be monitored to assess the necessity for a sample size increase. The decision to increase the sample size will be made by the sponsor when approximately 80% of the planned 240 randomized subjects are enrolled. The actual rate of drop-out subjects will be considered to assess the new number of subjects to be enrolled.

Subjects with brain metastasis will be randomized at a minimum of 20% of the second subset of subjects. Randomization will be stratified within brain metastasis (yes/no) in order to prevent unequal treatment allocation.

 CONFIDENTIAL	Protocol No. GDX-44-004 Version No. 2.0 (Protocol including amendment n°1) Date: 11 July , 2016	 Page 42 / 84
----------------------------------------------------------------------------------------------------------	----------------------------------------------------------------------------------------------------------	-----------------------------------------------------------------------------------------------------

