## 5.2. Data Sets Analysed and protocol deviations

### 5.2.1. Data Sets Analysed

There will be four subject sets defined for this study: the Extended Set, the Safety Set, the FAS and the PPS.

The Extended Set will include all subjects having signed the Informed Consent Form (ICF). This set will be used for subject disposition summaries, overall summary of AEs and individual listings.

The Safety Set will include all subjects, receiving at least one injection of contrast agent, regardless of the quantity. Subjects of subset 1 will be included in this set. This set will be used for description of demographic data, medical history, previous treatments and evaluation of safety. Analyses using the Safety Set will be based on the contrast agent actually received.

The FAS will include all subjects from subset 2 who have a CNR from both enhanced and unenhanced measurements derivable from one MRI by at least one off-site blinded reader. This set will be used for description of demographic data, baseline characteristics data, medical history, previous treatments and evaluation of efficacy. Analyses using the FAS will be based on the contrast agent allocated by the randomization whatever the contrast agent actually received, following the Intention To Treat (ITT) principle.

The PPS will be a subset of the FAS and will include all subjects who have no major protocol deviations (see below) throughout their whole study period. This set will be used for the evaluation of the primary efficacy criterion and main secondary criteria.

CONFIDENTIAL	
FORM
 
STATISTICAL ANALYSIS PLAN N° GDX-44-004
 
VERSION 1.0      DATED: 09JAN2018
	[REDACTED]
--------------	---	------------

Page 19 / 60

Analysis data sets will be presented on the Extended Set: subjects included in the Safety Set by contrast agent actually received and globally and included in the FAS and in the PPS by contrast agent allocated by the randomization and globally.

The tables and the listing that will be displayed are detailed in Sections 6.1.1.3 and 6.2.3.

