### 5.5.1.5 Selection Basis for Clinical Dose

The clinical dose will be selected according to the clinical benefit/risk ratio among the four doses evaluated based on the primary and secondary efficacy criteria analyzed in this study. A dose of P03277 which is not proved to be superior to the comparator on the primary criterion could however be recommended for use.

The table and the figures that will be displayed are detailed in Section 6.1.2.1.1 and the listings in Section 6.2.6.1.

CONFIDENTIAL	FORM	
STATISTICAL ANALYSIS PLAN N° GDX-44-004		Page 31 / 60
VERSION 1.0      DATED: 09JAN2018		

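### SAP 5.6 pools two differently allocated subsets in the safety dose columns, leaving four of the six between-dose contrasts, and each single dose against MultiHance, open to confounding by subset

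*SAP*

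**What the plan says.** Protocol 3.1 defines the training subset: "The first subset will consist of the first subject of each site". The allocation differs between the subsets. The protocol synopsis says "The randomization scheme will allocate subjects to the two P03277 treatment arms in a 1:1 ratio for the first subset of subjects", and then "to the four P03277 treatment arms in a 1:1:1:1 ratio for the second subset of subjects". Protocol 5.3.1 names the two arms of the first subset as 0.05 and 0.1 mmol/kg. It applies stratification by brain metastasis to subset 2 only.

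Subset 1 is left out of efficacy but counted for safety. SAP 5.2.1 says of the Safety Set: "Subjects of subset 1 will be included in this set". SAP 5.6 then lays out the results: "All safety parameters will be analyzed using the Safety Set on the following contrast agent groups", followed by the four P03277 doses, Total P03277 and MultiHance. Subjects enter a column by the agent they actually received. SAP 5.4 says the adverse event tables also show the period. Neither section mentions subset as a column, a row or an adjustment.

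Elsewhere the SAP does separate the subsets. Disposition (SAP 5.1) and protocol deviations (SAP 5.2.2) are each shown by subset.

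**The concern.** The chance of receiving a given dose depends on which subset a subject belongs to, and the safety tables ignore subset. A subject in subset 1 could not have been allocated to 0.025 or 0.2 mmol/kg, yet counts in the columns set beside those doses.

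The subsets also differ by design. Subset 1 takes one subject from every site whatever the site's size. That subject comes before the site qualification that Protocol 9.4.2 requires before enrolment continues. If first-at-site subjects have a different event rate, or their events are recorded differently, the gap would appear in the tables as a difference between doses.

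The planned baseline tables would only partly show this. SAP 5.4 describes study disease, including brain metastasis, on the Full Analysis Set, which excludes subset 1. Demographics, medical history and previous medications are shown on the Safety Set, but pooled across subsets.

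What is at stake is the safe half of the primary objective, a safe and effective dose. The safety tables are the main source for the risk side of the benefit/risk judgement among doses.

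**Working it through.** **Inputs.** Subset 2: 50 evaluable plus 10 extra subjects in each of four groups (Protocol 8). Subset 1: "maximum 40 subjects (depending of the number of participating sites) on the basis of 1 subject per site". Active centres: 28 (SAP 1.2). Allocation: as quoted above.

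**The plan's own total.** 4 × (50 + 10) = 240, and 240 + 40 = 280. This matches Protocol 8.

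**Share of subset 1 in each column.** Let s be the size of subset 1. The share is (s/2) / (60 + s/2) in the 0.05 and 0.1 columns, and s / (240 + s) in the Total P03277 and MultiHance columns.

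| Column | s = 40 | s = 28 |
|---|---|---|
| 0.025 | 0/60 = 0% | 0/60 = 0% |
| 0.05 | 20/80 = 25.0% | 14/74 = 18.9% |
| 0.1 | 20/80 = 25.0% | 14/74 = 18.9% |
| 0.2 | 0/60 = 0% | 0/60 = 0% |
| Total P03277 | 40/280 = 14.3% | 28/268 = 10.4% |
| MultiHance | 40/280 = 14.3% | 28/268 = 10.4% |

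**Which contrasts are affected.** Let p1 and p2 be the event rates in subsets 1 and 2, and w the share of subset 1. With no dose effect, a column shows p2 + w × (p1 − p2). Two columns A and B then differ by (wA − wB) × (p1 − p2).

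- 0.05 with 0.1: the shares are equal, so the term is zero.
- 0.025 with 0.2: both shares are zero, so the term is zero.
- 0.025 or 0.2 with 0.05 or 0.1 (four contrasts): 18.9% to 25.0% of p1 − p2.
- Total P03277 with MultiHance: the shares are equal, so the term is zero.
- 0.025 or 0.2 with MultiHance: 10.4% to 14.3% of p1 − p2 in size, with the dose column lacking subset 1.
- 0.05 or 0.1 with MultiHance: 18.9 − 10.4 = 8.5% to 25.0 − 14.3 = 10.7% of p1 − p2, in the opposite direction.

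The MultiHance lines assume that the subset difference is the same under both agents.

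**Illustration.** The documents give no value for p1 − p2. If it were 10 percentage points, the two middle doses would shift by 1.9 to 2.5 points against the lowest and highest. If it were 20 points, the shift would be 3.8 to 5.0 points. If it were zero, there would be no shift.

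**Cost of restricting to subset 2.** With no events in n subjects, the one-sided 95% upper bound is 1 − 0.05^(1/n). This is 4.9% for n = 60, 4.0% for n = 74 and 3.7% for n = 80.

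**The case against.** The strongest reply is that no formal safety comparison between doses is planned. SAP 5.6 contains counts, percentages, means and shift tables, with no between-dose test or estimate, and the stated safety objective compares P03277 with MultiHance. That is correct, and it limits the weight of the point. It does not remove it, because columns for four doses set side by side will be read against each other.

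A reader might infer that the whole between-dose safety comparison is non-randomised. The documents do not support that. Two of the six contrasts are untouched, including lowest against highest. At least 75% of every dose column comes from the four-arm randomisation. The artefact moves the two middle doses together, so it cannot by itself produce a steady trend across the four doses. The overall comparison with MultiHance is also balanced by subset, since every subject is planned to receive both agents in random order.

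A reader might also infer that the pooled tables drive the dose choice. SAP 5.5.1.5 opens: "The clinical dose will be selected according to the clinical benefit/risk ratio among the four doses evaluated". The same sentence goes on to rest the choice on the efficacy criteria, primary and secondary. Safety enters through the word risk, and no safety threshold or rule exists for the pooling to distort.

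The mechanism is also unproven. Both subsets meet the same eligibility criteria (Protocol 4), subset 1 has all the safety assessments (Protocol 3.1), and the blood tests and ECGs are assessed centrally. Even the worst illustrated shift, 5.0 points, is small beside sampling error. At assumed event rates of 10% to 20%, the 95% half-width for 60 against 80 subjects is 1.96 × √[p(1 − p)(1/60 + 1/80)], or about 10 to 13 points. This stands as an argument for low severity. Systematic confounding that can be removed at little cost is still worth removing.

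Finally, the SAP's table list and shells are not available here, so a by-subset safety display may exist in them. The text of SAP 5.4 and 5.6 provides for none.

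**Conclusion.** The point holds in a limited form. As written, SAP 5.6 mixes two randomisations with different allocation in single dose columns. Four of the six between-dose contrasts, and each single dose against the pooled MultiHance column, are therefore open to confounding by subset.

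The exposure is known and the resulting distortion is not. The shares assume full enrolment, an even split between arms, one subset 1 subject per centre, and dose received as allocated. The shifts in percentage points are illustrations, not estimates. This is a cheap improvement of minor severity to a descriptive display, and it does not invalidate the safety analysis.

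**What to change.** Keep the pooled Safety Set tables as planned, for overall incidence and rare events. Add to SAP 5.6 the main safety tables, at least the TEAE summaries, for subset 2 alone, with subset 1 shown separately. Follow the by-subset layout already used in SAP 5.1 and 5.2.2. State that between-dose safety, and each dose against MultiHance, will be read from the subset 2 tables, where all four dose groups come from one 1:1:1:1 randomisation.

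The cost is SAP wording and repeated tables, with no new data. In the subset 2 tables the 0.05 and 0.1 columns hold about 60 subjects instead of 74 to 80, so the zero-event upper bound is 4.9% rather than 3.7% to 4.0%. The pooled tables still count every subject, which respects the protocol's use of subset 1 for safety.

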### 1.1. Study objectives

The primary objective is to determine a safe and effective dose of P03277 based on a comparison of Contrast to Noise Ratio (CNR) between several doses, 0.025, 0.05, 0.1 and 0.2 mmol/kg of P03277 and MultiHance® at 0.1 mmol/kg.

The secondary objectives of the trial are:

- To assess technical adequacy of images.
- To evaluate capacity of lesion detection: number, size and location of lesions detected.
- To evaluate diagnostic information using lesion visualization variables (lesion border delineation, internal morphology and degree of contrast enhancement).
- To evaluate diagnostic confidence.
- To compare overall diagnostic preference between P03277 and MultiHance®.
- To assess P03277 dose/response relationship for CNR and lesion visualization variables.
- To evaluate the impact of P03277 and MultiHance®-enhanced MRI on subject treatment plan.
- To assess the safety profile of P03277 as compared to MultiHance® after intravenous administration.

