### Study arms:

## Two subsets of subjects:

- Subset 1: first subject of each study center randomized 1:1 as follows.
  - a. 0.05 or 0.1 mmol/kg Body Weight (BW) of P03277 then 0.1 mmol/kg of MultiHance® (1:1).
  - b. 0.1 mmol/kg of MultiHance® then 0.05 or 0.1 mmol/kg BW of P03277 (1:1).
- Subset 2: all subsequent subjects randomized 1:1 as follows.
  - a. 0.025, 0.05, 0.1 or 0.2 mmol/kg BW of P03277 then 0.1 mmol/kg of MultiHance® (1:1:1:1).
  - b. 0.1 mmol/kg of MultiHance® then 0.025, 0.05, 0.1 or 0.2 mmol/kg BW of P03277 (1:1:1:1).

CONFIDENTIAL	FORM	
	STATISTICAL ANALYSIS PLAN N° GDX-44-004	
	VERSION 1.0      DATED: 09JAN2018	Page 10 / 60

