#### 5.4. Demographic and Other Baseline Characteristics

Demographic data will be described using the FAS, the PPS and the Safety Set, medical history and previous medications will be described using the FAS and the Safety Set whereas other baseline characteristics will be described using the FAS only.

For tables described on the FAS (and the PPS if any, see Section 5.2.1), 5 columns will be displayed: "P03277 0.025 mmol/kg", "P03277 0.05 mmol/kg", "P03277 0.1 mmol/kg", "P03277 0.2 mmol/kg" and "Total", the dose being the one allocated by the randomization (either at the 1st or the 2nd period).

For tables described on the Safety Set, 7 columns will be displayed: "P03277 0.025 mmol/kg", "P03277 0.05 mmol/kg", "P03277 0.1 mmol/kg", "P03277 0.2 mmol/kg", "Total P03277", "MultiHance®" and "Total", the dose being the one actually received (either at the 1st or the 2nd period). It corresponds to the disposition of safety tables, except for tables of AEs in which period (MRI 1 and MRI 2) will appear also.

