### 5.6.2. Adverse Events

AEs will be coded using MedDRA dictionary version 20.1. The time period for the assessment of AEs is the time interval between the signature of the ICF and the subject's study end. AEs will be described systematically in terms of number and percentage of subjects with AEs and in terms of number of AEs. AEs will be displayed by period (MRI 1 and MRI 2) and overall.

TEAEs will be defined as follows:

- If the AE starts prior to the 1st injection then the AE is not emergent (pre-injection).
- If the AE starts after the 1st injection, then the AE is emergent (post-injection).
  - If it starts between the 1st injection and the 2nd injection (<), then it will be considered as an emergent AE associated with the 1st contrast agent of the subject's sequence.
  - If it starts after the 2nd injection ( $\geq$ ), then it will be considered as an emergent AE associated with the 2nd contrast agent of the subject's sequence.

CONFIDENTIAL	FORM	
STATISTICAL ANALYSIS PLAN N° GDX-44-004		Page 40 / 60
VERSION 1.0      DATED: 09JAN2018		

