## STATISTICAL ANALYSIS PLAN N° GDX-44-004

Page 42 / 60

VERSION 1.0

DATED: 09JAN2018

[REDACTED]

	SI units	Conventional units
Monocytes/Total Cells	%	%
Platelet count	10  /L	10  /µL
Hemoglobin	g/L	g/dL
Hematocrit	v/v	%
Mean Corpuscular Volume (MCV)	fL	fL

*Biochemistry data* from central laboratory include the following parameters:

	SI units	Conventional units
Sodium	mmol/L	mEq/L
Potassium	mmol/L	mEq/L
Chloride	mmol/L	mEq/L
Glucose	mmol/L	mg/dL
Blood Urea Nitrogen (BUN)	mmol/L	mg/dL
Urea	mmol/L	mg/dL
Serum creatinine	umol/L	mg/dL
eGFR	mL/min/1.73m 	mL/min/1.73m 
Total protein	g/L	g/dL
Calcium	mmol/L	mg/dL
Phosphorus	mmol/L	mg/dL
Total bilirubin	umol/L	mg/dL
Indirect bilirubin	umol/L	mg/dL
Conjugated bilirubin	umol/L	mg/dL
Aspartate Amino Transferase (AST)	U/L	U/L
Alanine Amino Transferase (ALT)	U/L	U/L
Alkaline Phosphatase	U/L	U/L
Lactate DeHydrogenase (LDH)	U/L	U/L
Triglycerides	U/L	U/L
Cystatin C	U/L	U/L

Hematology and biochemistry parameters at visits 2, 3, 4 and 5 will be described as quantitative variables in both SI and conventional units. Numbers and percentages of subjects with values out of range (lower than the lower limit or higher than the upper limit of quantification) will also be presented, except if values for normal ranges are unknown for a parameter.

Erythrocytes, neutrophils, eosinophils, basophils, lymphocytes, monocytes, hemoglobin and hematocrit (hematology) and potassium, chloride, BUN, urea, total protein, phosphorus, total bilirubin, AST, ALT, alkaline phosphatase, triglycerides and cystatin C (biochemistry) will be separately described by gender.

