## STATISTICAL ANALYSIS PLAN N° GDX-44-004

Page 43 / 60

VERSION 1.0

DATED: 09JAN2018

[REDACTED]

Change from baseline in *serum creatinine, eGFR, BUN and cystatin C* will be computed and described at visits 3, 4 and 5 in both SI and conventional units. The baseline value for each laboratory parameter will be the last value measured before the contrast agent administration (i.e. the assessment prior to 1st MRI).

Shift tables presenting relative change from baseline in classes *versus* baseline in classes will be displayed for *serum creatinine, eGFR, BUN and cystatin C*.

Baseline data will be classified as follows (no baseline categories will be used for cystatin C):

SI units	Conventional units

• Serum creatinine (umol/L):

○ < 20

○ <math>\geq 20</math> and < 40

○ <math>\geq 40</math> and < 60

○ <math>\geq 60</math>

• eGFR (mL/min/1.73m^2):

○ < 100

○ <math>\geq 100</math> and < 150

○ <math>\geq 150</math> and < 200

○ <math>\geq 200</math>

• BUN (mmol/L):

○ < 2

○ <math>\geq 2</math> and < 4

○ <math>\geq 4</math> and < 6

○ <math>\geq 6</math>

	

• Serum creatinine (mg/dL):

○ < 0.22

○ <math>\geq 0.22</math> and < 0.44

○ <math>\geq 0.44</math> and < 0.66

○ <math>\geq 0.66</math>

• eGFR (mL/min/1.73m^2):

○ < 100

○ <math>\geq 100</math> and < 150

○ <math>\geq 150</math> and < 200

○ <math>\geq 200</math>

• BUN (mg/dL):

○ < 12

○ <math>\geq 12</math> and < 24

○ <math>\geq 24</math> and < 36

○ <math>\geq 36</math>

Relative change from baseline will be calculated as follows:  $100^* \text{ (post injection measurement - baseline measurement) / baseline measurement}$ . Relative change from baseline will be classified as follows:

- $\leq -50\%$ .
- $> -50\%$  and  $\leq -25\%$ .
- $> -25\%$  and  $\leq -15\%$ .
- $> -15\%$  and  $< 0\%$ .
- $\geq 0\%$  and  $< 15\%$ .
- $\geq 15\%$  and  $< 25\%$ .
- $\geq 25\%$  and  $< 50\%$ .

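### The laboratory safety tables place each crossover completer under both agents and list results by visit, with no rule tying a value to the injection it follows

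*SAP*

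**What the plan says.** - **Columns.** SAP 5.6 applies one column rule to all safety parameters: "A subject will be included in a group as soon as he actually received the displayed contrast agent", whether at the first or the second period. The columns are the four P03277 doses, Total P03277 and MultiHance.
- **Period.** SAP 5.4 describes the Safety Set layout and adds: "It corresponds to the disposition of safety tables, except for tables of AEs in which period (MRI 1 and MRI 2) will appear also".
- **Laboratory rows.** SAP 5.6.4 states: "Hematology and biochemistry parameters at visits 2, 3, 4 and 5 will be described as quantitative variables". Changes in creatinine, eGFR, BUN and cystatin C "will be computed and described at visits 3, 4 and 5 in both SI and conventional units", and shift tables are planned for the same four parameters.
- **Laboratory baseline.** "The baseline value for each laboratory parameter will be the last value measured before the contrast agent administration", which 5.6.4 then specifies as the assessment before the first MRI. It therefore serves both periods.
- **Attribution.** SAP 5.6.2 has a rule for adverse events. If an event starts between the injections, "it will be considered as an emergent AE associated with the" first agent of the sequence; a later event goes to the second agent. SAP 5.6.4 has no counterpart for laboratory values.
- **Other safety data.** ECG, vital signs and injection-site tolerance (5.6.5.1 to 5.6.5.3) are set out by time from each injection.
- **Objective.** SAP 1.1 includes: "To assess the safety profile of P03277 as compared to MultiHance® after intravenous administration".

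**The concern.** Take a subject given MultiHance at visit 2 and P03277 0.2 mmol/kg at visit 4. The visit 3 creatinine can reflect MultiHance only. Under the stated rules the subject belongs to the P03277 0.2, Total P03277 and MultiHance columns, and nothing in 5.6.4 keeps the visit 3 value out of the first two. The visit rows do identify the period (visits 2 and 3 the first, visits 4 and 5 the second). They do not identify the agent given in that period, because this depends on the sequence and the laboratory section has no split by sequence.

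The shift tables have the same problem. A 15% to under 25% rise in creatinine at visit 3 would be counted under both agents once the subject receives the second injection.

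At stake is the laboratory part of the comparison with MultiHance, and of the benefit/risk judgement on which SAP 5.5.1.5 bases the choice of dose. A table that shows almost no difference because of its layout could be read as evidence of comparable renal safety.

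**Working it through.** The plan gives no figure for this, so there is none to reproduce. The check counts which values fall in which column if the text is followed literally.

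**Inputs**
- Sequence ratio 1:1. SAP 1.2, subset 2: "all subsequent subjects randomized 1:1 as follows", with P03277 first in one arm and MultiHance first in the other.
- n = 240 subset 2 subjects, 60 per dose (Protocol 8; SAP 3.3).
- q = share lost between the two injections. This is an assumption, from 0 to 10/60. The upper end borrows the allowance of 10 extra subjects per group of 60 for subjects who do not complete both MRIs.
- Loss is taken as equal in both sequences and unrelated to the laboratory value. Every subject injected at visit 2 is taken to have a visit 3 value.

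**Formulas**
- Total P03277 column = P03277-first subjects + MultiHance-first completers = n/2 + (n/2)(1 − q). The MultiHance column is the mirror image and has the same size.
- Subjects in both columns = n(1 − q).
- Share of visit 3 values that follow P03277: 1/(2 − q) in the P03277 column and (1 − q)/(2 − q) in the MultiHance column.
- Share of a true visit 3 difference that remains visible = 1/(2 − q) − (1 − q)/(2 − q) = q/(2 − q).

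**Results, n = 240**

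| q | Each column | In both | Overlap | After P03277: P03277 column | After P03277: MultiHance column | Difference visible |
|---|---|---|---|---|---|---|
| 0 | 240 | 240 | 100% | 50.0% | 50.0% | 0% |
| 5% | 234 | 228 | 97.4% | 51.3% | 48.7% | 2.6% |
| 10% | 228 | 216 | 94.7% | 52.6% | 47.4% | 5.3% |
| 10/60 | 220 | 200 | 90.9% | 54.5% | 45.5% | 9.1% |

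With the 280 subjects of both subsets the percentages are the same.

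**One dose column at visit 3.** With no loss, 30 of 60 values follow P03277 (50.0%). With q = 10/60, the column holds 30 + 25 = 55 subjects and 30/55 = 54.5% follow P03277. A contrast between two dose columns therefore keeps 50.0% to 54.5% of its true size.

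**Visit 5.** Only completers have a value, and every completer is in both columns. Total P03277 and MultiHance hold identical values whatever q is, so none of a true difference is visible.

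**If the shells split by record.** Visit 3 would be cleanly separated. The visit 5 change would still be the visit 5 value minus the visit 2 value, an interval that contains both injections. The visit 4 pre-dose change would describe the first agent, and the text does not say which column it would enter.

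**The case against.** The strongest reply is that the sentence in 5.6 sets who counts in a column and does not say that all of a subject's values go there. The same sentence governs the administration table (5.6.1.2), where printing a MultiHance volume under P03277 would make no sense. SAP 5.2.1 also bases Safety Set analyses on the agent actually received. The table list in SAP section 6 is blank in the public file and the shells are in a separate attachment, so a split by record cannot be ruled out. This stands as a statement of probable intent. It does not supply the missing rule for laboratory values, and it does not cure the single baseline.

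Several other points also stand:
- ECG, vital signs and injection-site tolerance are already organised by time from each injection, so the mixing shown above is confined to the laboratory tables.
- The tables are descriptive, with no test, and individual values are listed.
- Protocol 7.2.8 and 9.5.1 require clinically significant laboratory values to be reported as adverse events, and those are attributed by injection.
- Protocol 11.2 withholds the second injection after a creatinine or cystatin C rise of more than 25%. A subject withdrawn for that reason appears only under the first agent. The mixing therefore mainly affects smaller rises.

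A reader might infer that none of the non-AE safety tables can separate the agents, or that P03277 minus MultiHance is always exactly zero. The documents do not support either. The first extends the laboratory layout to sections written differently. The second holds at visit 3 only with no loss between injections. Nor are dose differences erased: the dose columns contain different randomised subjects, so a contrast between them is roughly halved at visit 3.

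**Conclusion.** The concern holds for the laboratory tables as the SAP text stands. Its size on the literal reading, with 1:1 sequences and an assumed, non-informative loss of 0 to 10/60 between injections:
- 50.0% to 54.5% of visit 3 values in a P03277 dose column follow P03277;
- 0% to 9.1% of a true difference between Total P03277 and MultiHance is visible at visit 3;
- none of that difference is visible at visit 5.

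If the unseen shells split by record, the visit 3 problem disappears. The narrower defect remains: visit 4 and 5 changes and shifts are measured from before the first injection and so carry any effect of the first agent.

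This should be fixed before the tables are run. It does not rank as a fatal flaw, because the summaries are descriptive, the individual data survive in listings, and clinically significant changes reach correctly attributed adverse event tables.

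**What to change.** In SAP 5.6 and 5.6.4:
1. State that each laboratory value is summarised under the agent most recently injected, as 5.6.2 does for adverse events. Visits 2 (pre-dose) and 3 go to the first agent; visits 4 (pre-dose) and 5 go to the second. Show the visit 4 pre-dose value also as late follow-up of the first agent.
2. Show period or sequence in these tables.
3. Compute change and shift tables from the pre-injection value of the same period (visit 2 or visit 4). Keep change from the first baseline as an additional display.

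In 5.6.5.1 and 5.6.5.2, add the same attribution and period-specific baseline sentence, since both sections now use only the value before the first injection. In 5.6.5.3 the attribution sentence alone is enough. Check the shells in the attachment against the revised text.

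The cost is SAP wording and table programming, with somewhat longer tables. No new data are needed: Protocol Table 1 already schedules laboratory samples, ECG and vital signs before each injection.
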